3. History of allergic reaction or intolerance to tetracycline antibiotics or any medical condition that would contraindicate the use of doxycycline including an increased risk of *C. difficile* infection, increases in BUN or an increased sensitivity to direct sunlight or ultraviolet radiation resulting in erythema (see doxycycline prescribing information in the Pharmacy Manual).
4. Has a need for any of the prohibited medications in [Section 6.5.1](#) or requires the medications/foods within the prohibited times in [Section 5.3.1.1](#).
5. Have a tattoo/scar/birthmark or any other skin condition affecting the deltoid area that may interfere with injection site assessments.
6. History of anthrax disease, suspected exposure to anthrax, or previous vaccination with any anthrax vaccine.
7. Have previously served in the military any time after 1990 or plan to enlist in the military any time from Screening through the final telephone contact.
8. Previous anaphylactic reaction, severe systemic response, or serious hypersensitivity to a prior immunization or a known allergy to synthetic ODNs, aluminum, formaldehyde, benzethonium chloride (phemerol).
9. Plan to have an elective surgery at any point during the study until after the final safety phone contact.
10. Have donated or plan to donate blood within one month prior to enrollment or at any point during the study until after the final safety phone contact.
11. Use of any investigational or non-registered product (drug, vaccine or biologic) within 30 days preceding the dose of study vaccine, or planned use during the study until after the final safety phone contact.
12. Planned administration of any commercially-available vaccine from one week prior to the first study vaccination through two weeks after the last vaccination.
13. Have experienced chronic dosing (defined as more than 14 days) with any immunemodifying drugs within six months of study enrollment. This includes oral, intramuscular, intra-articular, intravenous, or inhalation corticosteroids except in the case of inhaled or intranasal medications for seasonal allergies (see [Table 3](#)).
14. Receipt of immunoglobulins and/or any blood products within the three months preceding study enrollment or at any point during the study period until after the final safety visit on Day 51.

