15. An abnormal electrocardiogram (ECG) at screening interpreted as 'Abnormal, Significant'. Inclusion of participants with 'Abnormal, Insignificant' ECGs will be based on the principal investigator's discretion.
16. Have an active malignancy or history of metastatic or hematologic malignancy.

AV7909 Anthrax Vaccine

IND 014451

Protocol EBS.AVA.210, Version 3.0 (28 October 2019)

17. Have a history of an autoimmune, inflammatory, vasculitic or rheumatic or rheumatic disease including but not limited to systemic lupus erythematosus, Guillain-Barré syndrome, myasthenia gravis, polymyalgia rheumatica, diabetes mellitus type I, rheumatoid arthritis or scleroderma.
18. A positive laboratory evidence of hepatitis B, hepatitis C, or human immunodeficiency virus (HIV) HIV-1 or HIV-2 infection.
19. Positive result on urine drug screen, any evidence of ongoing drug abuse or dependence (including alcohol), or recent history (over the past five years) of treatment for alcohol or drug abuse.
20. Has an acute disease at the time of enrollment.

Note that screening lab tests may be delayed to allow the resolution of a transient acute condition or the subject may be rescreened according to procedures under [Section 5.4](#).

21. Any medical condition that, in the opinion of the investigator, could adversely impact the participant's involvement or the conduct of the study.
22. Have a significant chronic condition (see Sponsor's guidance on significant chronic conditions in [Appendix C](#)), eg, serious cardiovascular, pulmonary, hepatic, type II diabetes mellitus or renal disease that, in the opinion of the investigator, would render treatment unsafe or would interfere with trial evaluations or completion of the study.
23. An opinion of the investigator that it would be unwise to allow the participant to be randomized into the study.
24. Member or immediate family member of an investigator site team.

Investigational Products (IP), Dosage, Schedule and Mode of Administration:

- AV7909 (containing 0.5 mL AVA + 0.25 mg CPG 7909 adjuvant per dose) will be administered IM in the deltoid muscle of alternating arms to all (Groups 1 to 3) on Day 8 and Day 23.
- Ciprofloxacin (500 mg po q 12 hr) will be administered to participants in Group 1 on Days 4-9, Days 22-24, and Days 31-37.
- Doxycycline (100 mg po q 12 hr) will be administered to participants in Group 2 on Days 2-9, Days 22-24, and Days 32-38.

Duration of Treatment:

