To evaluate whether the administration of ciprofloxacin affects the immunogenicity of AV7909, TNA NF_{50} values two weeks after the second dose of AV7909 will be compared between the cohort of participants that received both ciprofloxacin and AV7909, ie, Group 1, also known as the ciprofloxacin test cohort, and the cohort who received AV7909 only, ie, Group 3 or the reference cohort. Point estimates and two-sided 95% lower CIs will be constructed for the ratio (test: reference) of geometric means. If the lower bound of the two-sided 95% lower CI is greater than 0.5 (the non-inferiority margin) it can be concluded that the immune response in the cohort who received AV7909 plus ciprofloxacin is non-inferior to the cohort which received AV7909 alone and thus that ciprofloxacin did not demonstrably affect the immunogenicity of AV7909.

The same evaluation will be conducted to determine if the administration of doxycycline affects the immunogenicity of AV7909 in that TNA NF_{50} values two weeks after the second dose of AV7909 will be compared between the cohort of participants that received both doxycycline and AV7909, ie, Group 2, the doxycycline test cohort, and the cohort who received AV7909 only (ie, Group 3 or the reference cohort). Point estimates and two-sided 95% lower CIs will be constructed for the ratio (test: reference) of geometric means. If the

AV7909 Anthrax Vaccine

IND 014451

Protocol EBS.AVA.210, Version 3.0 (28 October 2019)

lower bound of the two-sided 95% lower CI is greater than 0.5 (the non-inferiority margin) it can be concluded that the immune response in the cohort who received AV7909 plus doxycycline is non-inferior to the cohort which received AV7909 alone and thus that doxycycline did not demonstrably affect the immunogenicity of AV7909.

Sample Size Considerations

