6.5.1.1. Medications Prohibited Due to Effects on Inflammation or the Immune System

Prohibited and restricted medications for all participants include anti-inflammatory or antipyretic medications, topical antihistamine eye drops, nasal steroids, vaccines, immunosuppressive therapy, cytotoxic therapy and any experimental treatments (see [Table 3](#)).

Table 3: Medications Prohibited for all Participants

Category	Generic Name and Examples of Associated Brand Names
Anti-inflammatory or antipyretic medication: prohibited within 24 hours prior to or after vaccination	Glucocorticoids, aspirin-containing medication, NSAIDs, acetaminophen-containing medication Motrin, Advil [®] , Co-Advil [®] , Bayer [®] , Tylenol [®] Excedrin [®] Topical hydrocortisone Note: NSAIDs should be used (if medically indicated) with caution (outside 24 hours prior to or after vaccination) by participants in Group 1, because in pre-clinical studies and post-marketing the combination of high doses of quinolones with NSAIDs has been shown to provoke convulsions (see ciprofloxacin prescribing information in the Pharmacy Manual).
Aspirin withheld on each day of vaccination, but may be resumed the following day	Low-dose aspirin (≤ 81 mg/day)
Any commercially-available vaccine (except that for anthrax) through two weeks after the last vaccination	Including but not limited to vaccines for influenza, shingles, hepatitis B, pneumococcal, tetanus, yellow fever, pertussis, cholera, adenovirus, diphtheria, rabies virus haemophilus b, hepatitis A, human papillomavirus, measles, mumps, Japanese encephalitis virus, meningococcal vaccine, polio virus, plague, rotavirus, zoster vaccine, smallpox
Immunomodulatory agents through the final follow-up phone call. Note: inhalation use (eg, for seasonal allergies) is permitted.	Any systemic corticosteroids including, but not limited to, generic and brand names of: betamethasone, budesonide, cortisone acetate, dexamethasone, hydrocortisone, methylprednisolone, prednisolone, prednisone, triamcinolone.
Cytotoxic Therapy	Any of the alkylating agents, platinum coordinating complexes, antimetabolites or natural products used in current therapeutic regimens for cancer or rheumatic diseases including but not limited to generic and brand names of: methotrexate, cyclophosphamide, azathioprine, methotrexate, mercaptopurine, bendamustine, streptozocin, cisplatin, chlorambucil and hydroxyurea.

AV7909 Anthrax Vaccine

IND 014451

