6.5.1.2. Medications Known to Interact with Ciprofloxacin

Prohibited and restricted medications for participants in Group 1 include those that are primarily metabolized by human cytochrome 450P1A2 (CYP1A2), but also those that are metabolized by CYP3A4 since ciprofloxacin is a strong inhibitor of CYP1A2 and a moderate inhibitor of CYP3A4, as well as products that can affect the absorption of ciprofloxacin such as antacids, multivitamins, or supplements that contain magnesium, aluminum, calcium, iron or zinc. If required, the latter medications should be taken 2 hours before or 6 hours after a ciprofloxacin dose. Refer to the ciprofloxacin prescribing information (in the Pharmacy Manual) where medications which are known to interact with ciprofloxacin are listed and should not be taken by participants in Group 1 of this study.

A more extensive list of medications is provided at the following URL:

<https://online.epocrates.com/drugs/50110/ciprofloxacin/Monograph> {Athenahealth 2019a}. With the exception of those indicated to be contraceptives and those which may be components of antacids, multivitamins, or supplements that contain magnesium, aluminum, calcium, iron, or zinc, all medications, vaccines and supplements found at the above URL are also prohibited for participants in Group 1 of this study.

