6.5.1.3. Medications Known to Interact with Doxycycline

Prohibited and restricted medications for participants in Group 2 can be found in the doxycycline prescribing information (provided in the Pharmacy Manual)**Error! Reference source not found.** A more extensive list of medications is provided at the following URL:

<https://online.epocrates.com/drugs/20310/doxycycline/Monograph> {Athenahealth 2019b}. With the exception of those indicated to be contraceptives and those which may be components of antacids, multivitamins, or supplements that contain magnesium, aluminum, calcium, iron, or zinc, all medications, vaccines and supplements found at the above URL are also prohibited for participants in Group 2 of this study.

AV7909 Anthrax Vaccine

IND 014451

Protocol EBS.AVA.210, Version 3.0 (28 October 2019)

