10.3. Analysis Populations

There will be four analysis populations for this study:

The Intent-to-treat (ITT) Population will include all participants who are randomized. Participant disposition and baseline demographics will be summarized by IP group (Groups 1, 2 and 3) for the ITT population according to the group into which the participant is randomized.

The Safety Population will include all randomized participants who receive at least one dose of either antibiotic or AV7909. All the safety analyses will be conducted with the Safety Population according to the treatment they received.

The PK Population will include all participants in Group 1A and Group 2A who:

- Received two doses of AV7909 according to the protocol (eg, correct dose no temperature excursion, and within the study-specified windows)
- If in Group 1A, received at least 5 of the 7 in-clinic ciprofloxacin doses between Day 4 through the morning of Day 8 and between Day 31 through the morning of Day 35; or if in Group 2A, received at least 7 of the 9 in-clinic doxycycline doses between Day 2 through the morning of Day 8 and between Day 32 through the morning of Day 38
- Have adequate data for PK analysis for the calculation of AUC_{0-12h} and C_{max} at the Day 8 (both Group 1A and 2A) and Day 35 (Group 1A) or Day 38 (Group 2A) visits,
- Have no protocol deviations that would affect ciprofloxacin or doxycycline PK

Exclusion of participants from population will be done on a case-by-case basis at the time of the PK parameter analysis.

The PK Population will be used for all PK analyses. Participants will be included in the treatment group (ciprofloxacin or doxycycline) according to the antibiotic they received.

The Immunogenicity Population will include all randomized participants who meet the following criteria:

- Received two AV7909 vaccinations according to the protocol (eg, correct dose, no temperature excursion, and within the study-specified windows)

AV7909 Anthrax Vaccine

IND 014451

Protocol EBS.AVA.210, Version 3.0 (28 October 2019)

- Had a valid immunogenicity (TNA) result at Day 1 (pre-vaccination) showing no evidence of previous exposure to anthrax or an anthrax vaccine (ie, TNA below the limit of detection)
- Had a valid immunogenicity (TNA) result at Day 37, within the study specified window
- Participants in Group 1 or 2 should have taken at least 50% of the protocol-specified antibiotic doses

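### The plan does not clearly keep ciprofloxacin or doxycycline users out of the Group 3 reference arm of the TNA non-inferiority test

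*Protocol*

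**What the plan says.** **Entry.** Criterion 4 (Synopsis and Protocol 5.2) excludes anyone who "Has a need for any of the prohibited medications in" Section 6.5.1. The criteria nearest to antibiotic use are 13 ("Have experienced chronic dosing (defined as more than 14 days) with any" immune-modifying drug, with corticosteroids named) and 20 ("Has an acute disease at the time of enrollment"). Neither mentions antibiotics.

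**Prohibited medications.** Section 6.5.1.1 and Table 3 bind everyone: "Prohibited and restricted medications for all participants include anti-inflammatory or antipyretic medications, topical antihistamine eye drops, nasal steroids, vaccines, immunosuppressive therapy, cytotoxic therapy" and experimental treatments. Table 3 adds anticoagulants for Groups 1A and 2A, and immunoglobulins or blood products. It lists no antibacterial class. The other two lists are addressed by group: "Prohibited and restricted medications for participants in Group 1 include those that are primarily metabolized by human cytochrome" enzymes (6.5.1.2), and "Prohibited and restricted medications for participants in Group 2 can be found in the doxycycline prescribing information" (6.5.1.3). Both refer to the Pharmacy Manual and a web page.

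**Analysis.** The test compares each antibiotic group with "the cohort who received AV7909 only, ie, Group 3 or the reference cohort". The only antibiotic condition in the Immunogenicity Population is "Participants in Group 1 or 2 should have taken at least 50% of the protocol-specified antibiotic doses"; SAP 3.2 has the same rule. The PK Population does have a clause on deviations that would affect the result. The SAP version of that clause mentions immunogenicity results, but it sits in the PK Population, which contains only Groups 1A and 2A.

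**The concern.** The immunogenicity question is antibiotic against no antibiotic. Protocol 4.3.2 and 4.3.3 give reasons why each drug might affect the antibody response. If the reference arm includes people taking the tested drug and that drug lowers TNA, the Group 3 geometric mean falls and the ratio rises toward 1. In a superiority test this kind of dilution is conservative. In a non-inferiority test it works against the 2.5% error rate. Nothing in the SAP would correct it: the main analysis (SAP 7.2) is unadjusted, and the exploratory model (SAP 7.2.1) adds only site, sex and age.

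**Working it through.** **Inputs.** From Protocol 10.2 and SAP 2.4: margin 0.5, one-sided 2.5%, true ratio 0.85, CV 100%, 53 evaluable per group, 70 planned. The documents give no rate of antibiotic use in Group 3. The fraction p is therefore assumed, over a range of 2% to 10%.

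**The plan's own figure.** The log-scale SD is sqrt(ln(1 + 1²)) = sqrt(ln 2) = 0.8326. The distance to the margin is ln(0.85/0.5) = 0.5306. With 53 per group the noncentrality is 0.5306 / (0.8326 × sqrt(2/53)) = 3.28, and the noncentral t with 104 df gives power 90.2%. With 52 per group it is 89.6%. The stated 53 reproduces.

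**Effect of users in the reference arm.** Let θ be the true ratio, and let a fraction p of Group 3 carry the full log effect ln θ. Then:

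- expected log contrast = ln θ − p ln θ = (1 − p) ln θ, so the expected ratio is θ^(1−p);
- Group 3 variance = 0.6931 + p(1 − p)(ln θ)²;
- SE = sqrt((0.6931 + Group 3 variance)/n);
- error rate = P(noncentral t on 2n − 2 df exceeds its 97.5% critical value), with noncentrality [(1 − p) ln θ − ln 0.5]/SE.

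For θ at or below the margin, θ^(1−p) is largest at θ = 0.5, so that is the worst null case. Example for p = 5%, n = 53: shift = 0.05 × 0.6931 = 0.0347; Group 3 variance = 0.6931 + 0.0475 × 0.4805 = 0.7160; SE = sqrt(1.4091/53) = 0.1631; noncentrality = 0.21; error rate = 4.0%.

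| Assumed p | Expected ratio when truth is 0.5 | Error, n = 53 | Error, n = 70 |
|---|---|---|---|
| 0 | 0.500 | 2.5% | 2.5% |
| 2% | 0.507 | 3.0% | 3.1% |
| 5% | 0.518 | 4.0% | 4.3% |
| 10% | 0.536 | 6.2% | 7.0% |

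A simulation with 100,000 runs at n = 53 gave 2.4%, 3.9% and 6.1% for p = 0, 5% and 10%.

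**Scale.** At n = 53, 2% is about one person (0.02 × 53 = 1.06). If users carry half the log effect, the shift is p/2 × 0.6931, so p = 10% behaves about like p = 5%, roughly 4.0%. At the planning ratio of 0.85 the expected ratio moves only to 0.85^0.95 = 0.857 (p = 5%) or 0.85^0.90 = 0.864 (p = 10%). At θ = 1 it does not move.

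**The case against.** A reader might infer that a volunteer on long-term doxycycline is sure to pass screening. The documents do not establish that. Criterion 4 is applied before randomization, when no group exists, and it cites the whole of Section 6.5.1. On its face that takes in the two interaction lists, whose contents cannot be seen here. Appendix C points the other way, because for chronic conditions it ties prohibited medication to Table 3. The two passages leave the matter open.

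A reader might also infer that a Group 3 user commits no deviation and is certain to be analysed as vaccine only. That is too categorical. Table 3 bars products used in a clinical investigation, and the protocol calls both antibiotics investigational products. The population also groups people by the treatment they actually received. Neither text says how to treat an outside prescription, so the plan is ambiguous at this point.

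There is partial protection:

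- Participants must be healthy, and criteria 21 to 23 give the investigator discretion. Medications are recorded at Screening and on Day 1, before the eligibility review.
- Protocol 6.1.4 deals with illness in the three days before each vaccination. A participant who misses the second-vaccination window fails the two-vaccination criterion.
- SAP 8.5 tabulates concomitant medications by treatment group, so use in Group 3 would be visible.

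All of this stands and makes high contamination unlikely. None of it addresses a course taken between the vaccinations, or from Day 24 to Day 37, and none of it changes who enters the test.

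The illustration is also a worst case for a given p. It needs a true ratio at the margin and every user carrying the full effect of the scheduled regimen. A Group 3 doxycycline user need not carry the ciprofloxacin effect. The endpoint is secondary and is tested formally only after the PK endpoint is met.

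**Conclusion.** The gap holds in a limited form. No criterion clearly bars current antibiotic use. The Immunogenicity Population has no condition on ciprofloxacin or doxycycline use in Group 3, and no deviation clause that could reach that group. If such use occurs and the drug lowers TNA, the bias favours non-inferiority. For p of 2% to 10% the upper-bound error is about 3.0% to 6.2% with 53 per group, against 2.5%. It is lower with partial effects or a different antibiotic, and there is no bias without a true effect.

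It would be wrong to conclude that the reference arm is contaminated or that the 2.5% level is lost. Both depend on a rate of use and a drug effect that the documents do not give. The primary PK comparisons do not use Group 3 and are untouched. The repair is worth making because it is cheap and uses data already collected.

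**What to change.** 1. In the exclusion criteria (Synopsis and Protocol 5.2), state that a volunteer taking a systemic antibiotic at Screening or Day 1 is not eligible. This helps only for people not yet enrolled.
2. In the Immunogenicity Population (Protocol 10.3 and SAP 3.2), add for Group 3: *no systemic ciprofloxacin or doxycycline, or other fluoroquinolone or tetracycline, from Day 1 through the Day 37 TNA draw*, determined from recorded concomitant medications. Limiting this to the two drug classes keeps to the plan's own rationale; a ban on every antibacterial would go beyond it.
3. In SAP 7.2, report the non-inferiority confidence interval with and without this criterion. The exclusion comes after randomization and is linked to infection, so the reader needs to see whether it changes the result.

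**Cost.** One eligibility sentence, one population criterion and one repeated interval. A few Group 3 participants may leave the immunogenicity analysis, within the 25% allowance (70 − 53 = 17 per group). The sample size does not change. Treatment of infections is not restricted, and affected participants stay in safety follow-up.

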2. INTRODUCTION

2.1. Study Rationale

Antimicrobial therapy is an important component of post-exposure prophylaxis (PEP) following exposure to aerosolized *Bacillus anthracis* spores. According to the Centers for Disease Control and Prevention's (CDC) Advisory Committee on Immunization Practices (ACIP) recommendations for PEP of inhalation anthrax, BioThrax[®] (Anthrax Vaccine Adsorbed; AVA) administered subcutaneously at 0, 2, and 4 weeks, combined with appropriate antimicrobial therapy, is currently licensed for this indication in previously unvaccinated adults {Wright et al, 2010}. While a two-dose vaccination schedule with AV7909 for PEP would have clear logistical advantages over the three-dose schedule with BioThrax, antimicrobial therapy would still be a required component of the PEP schedule. The purpose of this study is to identify any potential effects of AV7909 vaccination on the PK of the antibiotics ciprofloxacin or doxycycline and any potential effects of ciprofloxacin or doxycycline therapy on the immunogenicity of AV7909. Both ciprofloxacin and doxycycline have been chosen for use in this study because they are first-line therapies recommended by the ACIP for PEP {Wright et al, 2010}.

2.2. Background

Anthrax is an acute non-communicable infectious disease caused by *B. anthracis*, a spore-forming, gram-positive bacterium that occurs globally {Brachman et al, 2008; WHO, 2008}. While human cases are rare in the United States (US), the bioterrorist use of *B. anthracis* spores as a biological weapon resulted in the exposure of tens of thousands of individuals across six states and the District of Columbia in 2001 {CDC, 2001}. The CDC considers *B. anthracis* to be one of the most likely biological agents to be used in any future terrorism activities {CDC, 2014}.

While vaccination prior to exposure offers the optimal protection against anthrax, mass vaccination is neither practical nor feasible as a defense against bioterrorism {CDC, 2000}. At the time of the bioterrorist events in 2001, the only Food and Drug Administration (FDA)-approved post-exposure treatments for anthrax were the antimicrobials: ciprofloxacin, ofloxacin, doxycycline, penicillin VK and amoxicillin {CDC, 2000}. In the event of an aerosol exposure, the CDC's ACIP recommended at the time that PEP consist of a minimum of 30 days of antibiotics and possibly a longer course of 42-60 days. The ACIP recommendations from 2000 also stated that if a vaccine was available, three doses of vaccine should be administered (at 0, 2, and 4 weeks) with discontinuation of antibiotic after the third vaccination {CDC, 2000}.

In response to the 2001 attacks, approximately 9300 individuals were initially prescribed antimicrobial prophylaxis for at least 60 days; however, a subsequent study determined that compliance with this schedule was poor. Based on interviews with 6178 persons, 86% (n=5343) took at least one dose of antimicrobial prophylaxis but fewer than half (44%, n=2712) reported taking antimicrobial prophylaxis for at least 60 days {Shepard et al, 2002}.

AV7909 Anthrax Vaccine

IND 014451

Protocol EBS.AVA.210, Version 3.0 (28 October 2019)

The CDC subsequently offered an additional antimicrobial treatment in a voluntary treatment continuation program with or without three doses of the BioThrax vaccine; about 200 opted to receive the supply of antimicrobials plus three doses of BioThrax {Tierney et al, 2003}.

Ultimately, the attacks resulted in 22 cases of anthrax; 11 cutaneous and 11 inhalation, five of which (all inhalation cases) resulted in mortality {Jernigan et al, 2002}. No cases of anthrax were identified among persons recommended to take antimicrobial prophylaxis after the bioterrorist attacks of 2001 {Tierney et al, 2003}.

In November of 2015, the FDA approved BioThrax for PEP given in three doses (administered at 0, 2, and 4 weeks) along with a post-exposure regimen of appropriate antimicrobial prophylaxis. {Wright et al, 2010} However, in contrast to the ACIP's earlier recommendation, which indicated that antimicrobial prophylaxis could cease after the third dose of vaccine {CDC, 2002}, the ACIP updated their recommendations to reflect a 60-day antimicrobial treatment period and to continue with the antimicrobial for 14 days following the third dose of vaccine, which could result in the antimicrobial being used for more than 60 days, if the initiation of the vaccination series was delayed.

Given the poor compliance with an antimicrobial regimen of 60 days as observed in 2001, there is a demonstrated medical need for a vaccine that can induce a rapid and robust immune response. AV7909, a vaccine consisting of AVA plus the adjuvant CPG 7909, is under development to meet this need. CPG 7909 is a synthetic immunostimulatory oligonucleotide (short DNA sequence). It has been shown to be a toll-like receptor 9 (TLR9) agonist that induces both an enhanced antigen-specific antibody response and a natural killer (NK) T-cell immune response when used in combination with prophylactic (preventative) or therapeutic vaccines {Krieg, 1996; Pissetsky, 1996; Kim et al, 1999; Stewart et al, 2008}.

By combining AVA with CPG 7909, the AV7909 product development program aims to create a new vaccine that will accelerate the development of the immune response to the *B. anthracis* antigens, reducing the number of doses required to induce full protection, thereby reducing the amount of antigen required to establish protective immunity. From the three clinical studies conducted to date, Study V011, Study EBS.AVA.201 and Study EBS.AVA.208 {Rynkiewicz et al, 2011; Hopkins et al, 2013; Hopkins et al, 2016}, a formulation consisting of 0.5 mL of AVA plus 0.25 mg CPG 7909 administered intramuscularly (IM) on a 0, 2 week schedule has been selected as the candidate formulation for Phase 3.

Based on the results of the last study, vaccination of healthy adults with 2 doses of AV7909 can potentially accelerate the development of a protective level of immunity by one or two weeks (in comparison to the time required with the 3-dose schedule of BioThrax) depending on whether AV7909 doses are administered four weeks or two weeks apart {Hopkins et al, 2016}. This study also demonstrated that AV7909 given in a 3-dose schedule (as per the BioThrax label) resulted in a greater percentage of individuals achieving a potentially protective antibody level one week after the last vaccination and at all subsequent time points evaluated.

A clinical trial conducted with BioThrax and ciprofloxacin {EPDG, 2014} as part of the process of PEP licensure found no evidence of any interaction between vaccination with BioThrax and the pharmacokinetics (PK) of ciprofloxacin or between dosing with ciprofloxacin and the immunogenicity of BioThrax. It is the goal of this trial to demonstrate that vaccination with

AV7909 Anthrax Vaccine

IND 014451

Protocol EBS.AVA.210, Version 3.0 (28 October 2019)

AV7909 does not affect the PK profiles of either ciprofloxacin or doxycycline and that neither ciprofloxacin nor doxycycline impair the immunogenicity of AV7909.

